### **3.8.2.4 Xiaomi Smart Band (Measure heart rate, exercise intensity)**

Heart rate monitoring devices, such as the Xiaomi Smart Band, are commonly used to measure exercise intensity. The device is securely worn on the wrist. Before testing, participants undergo a 5-minute resting period to record their resting heart rate (RHR) as baseline data. During exercise, the device continuously records heart rate, activity duration, step count, calories burned, and distance covered (Concheiro-Moscoso et al., 2022). Depending on the type of exercise, such as running or interval training, the appropriate mode is selected to monitor heart rate in real time and assess intensity levels. These intensity levels are categorized into low intensity (50–60% of maximum heart rate, MHR), moderate intensity (60–70% of MHR), and high intensity (70–85% of MHR). For interval training, the device tracks heart rate fluctuations during different intensity phases. After the exercise, the ending heart rate (EHR) is recorded, and heart rate recovery (HRR) is monitored during a 5-minute cooldown period. By analyzing metrics such as average heart rate (AHR), maximum heart rate (MHR), and recovery rate, a comprehensive understanding of physiological responses and fitness levels can be obtained (Bravi et al., 2023).

The purpose of testing exercise intensity is to optimize training efficiency, evaluate cardiovascular function, ensure safety, monitor progress, and personalize training plans. By identifying different intensity zones, it is possible to target specific fitness goals, such as improving aerobic or anaerobic capacity, while minimizing risks and avoiding overtraining. This method provides data-driven personalized training strategies that not only enhance performance but also effectively monitor long-term fitness progress (Lugones-Sanchez et al., 2022).

Figure 14 Xiaomi Smart Band

### 3.8.3 Data analysis

To ensure the reliability and validity of the collected data, an effective database will first be established by importing the experimental data into an Excel spreadsheet. Subsequently, SPSS 29.0 software will be utilized for comprehensive statistical analysis.

Following this, a series of detailed statistical analyses will be conducted on the data related to jump performance and stability of beginner gymnasts. These analyses include:

1. Descriptive statistics to summarize the central tendencies and variability in the data.
2. Demographic variable analysis to explore the influence of participants' characteristics (e.g., age, BMI, or gender) on the outcomes.
3. Correlation analysis to examine the relationships between key variables, such as balance training methods and improvements in jump performance and stability.
4. Factor analysis to identify the underlying factors contributing to the observed improvements, thereby determining the most significant influencing variables.

This multi-layered analysis ensures a thorough understanding of the data and provides robust evidence for identifying the most effective training strategies for enhancing the jumping and stability performance of beginner gymnasts. Through this systematic approach, the research aims to generate scientifically valid and practically applicable insights.

## CHAPTER 4

### 4.0 EXPECTED RESULTS

#### 4.1 Anthropology

Table 16 Height, weight, and BMI at baseline and after 8 weeks in the static, dynamic, static and dynamic intervention and control groups. Data presented as mean  $\pm$  SD.

Anthropometry	Groups								Two-way repeated measures ANOVA					Bonferroni ( $p$ )		
	Static		Dynamic		Static + Dynamic		Control									
	B	W8	B	W8	B	W8	B	W8	SS	df	MS	F	$p$			
Height																
Weight (kg)																
BMI ( $\text{kg}/\text{m}^2$ )																

B= Baseline, W=Week, ANOVA= Analysis of variance; SS=Sum of squares; df= degrees of freedom, MS=Mean square, F= F-test statistical value,  $p<0.05$

denotes significance difference

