## **1.5 HYPOTHESES OF THE STUDY**

Statistical Hypotheses for the First Part:

HA1: There is a significant improvement in the stability of beginner gymnasts (as measured by the 8-Point Star Offset Test) following static balance training, dynamic balance training, or combined static-dynamic balance training interventions.

H01: There is no significant improvement in the stability of beginner gymnasts (as measured by the 8-Point Star Offset Test) following static balance training, dynamic balance training, or combined static-dynamic balance training interventions.

Statistical Hypotheses for the Second Part:

HA2: There is a significant improvement in the jumping skills of beginner gymnasts (as measured by Countermovement Jump and Single-leg Countermovement Jump) following static balance training, dynamic balance training, or combined static-dynamic balance training interventions.

H02: There is no significant improvement in the jumping skills of beginner gymnasts (as measured by Countermovement Jump and Single-leg Countermovement Jump) following static balance training, dynamic balance training, or combined static-dynamic balance training interventions.

Statistical Hypotheses for the Third Part:

HA3: Static balance training, dynamic balance training, or combined static-dynamic balance training significantly enhances gymnastic performance movements (as measured by Standing Single-leg 360 ° turn and Straight jump 360 ° turn), as captured using 3D motion capture technology.

H03: Static balance training, dynamic balance training, or combined static-dynamic balance training does not significantly enhance gymnastic performance movements (as measured by Standing Single-leg 360 ° turn and Straight jump 360 ° turn), as captured using 3D motion capture technology.

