### **3.6 Sample Size Estimation**

Using G - power 3.1 (Figure 10), the study focuses on time (within - subject factor), group (between - subject factor), and their interaction effects. The effect size is set to medium (0.35), with an alpha value of 0.05 and a statistical power of 0.80. A total of four groups will be included (static balance, dynamic balance, combined static and dynamic balance, and a control group), with measurements conducted twice, pre - and post - intervention. The calculated sample size is 52 participants. Considering a dropout rate of 15%, 60 participants will be recruited. Participants will be randomly assigned to four groups, with 15 participants in each group. Since the total dropout rate applies uniformly and participants are equally distributed across the four groups, each group's dropout rate is also 15%.

[figure not shown]

Figure 10 Flow chart of the G-power

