## 4.2 Jumping ability test results

Table 17 Countermovement jump (CMJ) and single-leg countermovement jump tests at baseline and after 8 weeks in the static intervention, dynamic intervention, static-dynamic intervention, and control groups. Data presented as mean  $\pm$  SD.

Group	Test Type	Time Point	Jump Height (Mean $\pm$ SD)	Peak Force (N) (Mean $\pm$ SD)	Rate of Force Development (N·s) (Mean $\pm$ SD)	Impulse (N·s) (Mean $\pm$ SD)	Two-Way Repeated Measures ANOVA	Bonferroni (p)
Static balance group	Countermovement jump	B						
		W8						
	Single-leg countermovement jump	B						
		W8						
Dynamic balance group	Countermovement jump	B						
		W8						
	Single-leg countermovement jump	B						
		W8						
Static and Dynamic balance group	Countermovement jump	B						
		W8						
	Single-leg countermovement jump	B						
		W8						
Control group	Countermovement jump	B						
		W8						
	Single-leg countermovement jump	B						
		W8						

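### HA1–HA3 name test batteries, not a deciding measure, contrast or rule, so how 19 outcomes tested at 0.05 settle three hypotheses can be chosen after the data are seen

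*Protocol*

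**What the plan says.** - **Hypotheses (section 1.5).** HA2 reads "There is a significant improvement in the jumping skills of beginner gymnasts (as measured by Countermovement Jump and Single-leg Countermovement Jump"), following static, dynamic or combined training. HA1 has the same form for the 8-point star test, and HA3 is similar for the two 360° turns. None names a single measure, a comparison with control, or the number of results that must be significant.
- **Outcomes (sections 4.2 to 4.4).** Table 17, titled "Countermovement jump (CMJ) and single-leg countermovement jump tests at baseline and after 8 weeks", lists four measures for each of two jumps. Table 18 lists three stability measures. Tables 19 and 20 list four measures each. Every table has a column headed "Two-Way Repeated Measures ANOVA" and a Bonferroni column beside it.
- **Level.** Section 3.6 states: "The effect size is set to medium (0.35), with an alpha value of 0.05 and a statistical power of 0.80". The Table 16 footnote says that p<0.05 "denotes significance difference". Tables 17–20 print no threshold.
- **Target effect (section 3.6).** "the study focuses on time (within - subject factor), group (between - subject factor), and their interaction effects". No outcome is named.
- **Analysis text (section 3.8.3).** It lists descriptive, demographic, correlation and factor analyses. It gives no rule for deciding HA1–HA3.

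**The concern.** A hypothesis defined by a battery can be settled in several ways: by one chosen measure, by any significant measure, by at least one in each test, or by all of them. The word joining the three programmes is *or*, so it is also open whether one programme is enough. Because improvement is described as following training, without mention of control, a time effect could be offered as support in place of the time-by-group interaction.

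These choices have very different error rates. If the protocol does not make the choice, the supporting measure, contrast and rule can follow the results. The trial could then report a hypothesis as confirmed on its best-looking measure, and a reader could not tell what error rate applied.

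**Working it through.** **Inputs**
- Outcomes: Table 17, 4 measures × 2 jumps = 8 (HA2). Table 18, 3 (HA1). Tables 19 and 20, 4 + 4 = 8 (HA3). Total 8 + 3 + 8 = 19. A time-by-group ANOVA takes one dependent variable, so this means 19 ANOVAs.
- Level 0.05, effect size f = 0.35, four groups, two time points, N = 52 (section 3.6).
- Assumed, because the protocol text gives neither: correlation between outcomes r from 0 to 0.9, and correlation ρ between the two time points of 0 or 0.5. Figure 10 is not shown.

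**1. Reproducing the plan's figure.** Section 3.6 says: "The calculated sample size is 52 participants". For the interaction, the noncentrality is λ = f²·N·m/(1−ρ) with 3 and N−4 degrees of freedom. With ρ = 0 and N = 52, λ = 0.1225 × 52 × 2 = 12.74 and power is 0.831. The next smaller balanced size, 48, gives 0.794. So 52 is reproduced exactly at ρ = 0, for one test at the full 0.05.

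**2. If any significant outcome counts.** With k independent interaction tests, the chance of at least one false positive is 1 − 0.95^k:
- HA1: 1 − 0.95³ = 0.143
- HA2 or HA3: 1 − 0.95⁸ = 0.337
- all outcomes: 1 − 0.95¹⁹ = 0.623

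For correlated outcomes I simulated the 3-df group F test on change scores (13 per group, equal correlation, 20,000 runs):

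| r (assumed) | 3 outcomes | 8 outcomes | 19 outcomes |
|---|---|---|---|
| 0.3 | 14% | 31% | 54% |
| 0.5 | 13% | 26% | 43% |
| 0.7 | 11% | 20% | 31% |
| 0.9 | 8% | 12% | 16% |

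Repeat runs differ by about one percentage point.

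**3. If HA2 or HA3 needs a hit in both of its tests.** With four outcomes per test and independence, the rate is (1 − 0.95⁴)² = 0.1855² = 0.034. In the same simulation it is about 6% at r = 0.5 and 7% at r = 0.7 and 0.9. The range is therefore about 3–7%.

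**4. Cost of controlling three tests.** Holm's strictest step is 0.05/3 = 0.0167. Power for the interaction at f = 0.35:

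| ρ (assumed) | N = 52, 0.05 | N = 52, 0.0167 | N for 80% at 0.0167 |
|---|---|---|---|
| 0 | 0.83 | 0.69 | 64 |
| 0.5 | 0.99 | 0.97 | 36 |

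**The case against.** **The protocol never says that one significant result confirms a hypothesis.** This is correct. HA2 and HA3 join their two tests with *and*, and on that reading their rate is close to nominal. A reader might infer an any-one-of-eight rule with a 34% error rate, but the text does not support that as the plan's rule. What stands is that no rule is fixed.

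**A false positive is not shown to be likely.** Also correct. The rate across 19 outcomes exceeds one half only with independent or weakly correlated outcomes. These outcomes are related: section 1.6 says that net impulse determines jump height. At r of 0.5 or more the any-outcome rate falls to 43% or less, though it stays well above 5%.

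**The p<0.05 footnote belongs to the anthropometry table, and Chapter 4 holds empty tables.** True. Applying 0.05 to the 19 outcomes is an inference. It rests on section 3.6, which gives only this level, and on the same ANOVA and Bonferroni columns recurring in Tables 17–20.

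**Bonferroni is planned.** A column exists, but its family is not defined. Its place beside the ANOVA column suggests post hoc group comparisons within an outcome, which would not limit error across outcomes. The text does not settle this.

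**A statistical analysis plan may handle multiplicity, and part of section 3.2.1 is not in the text reviewed.** Adjustment detail can properly sit in an analysis plan, and its absence here is not the point. The hypotheses are fixed in this protocol, however, and they are worded so that no result clearly decides them.

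**Conclusion.** The point holds as a gap in the decision rule. HA1–HA3 rest on 3, 8 and 8 outcomes and three programmes joined by *or*. In the text shown, no measure, contrast or count is named, and 0.05 is the only level. Depending on which rule is adopted later, the false-positive rate for HA2 or HA3 runs from about 3–7% (a hit in both tests) to 34% (any of eight, independent) or about 26% (any of eight, r = 0.5). For HA1 the any-outcome rate is about 13–14% at r up to 0.5.

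These figures assume that all nulls are true, that only interactions are counted, and that outcomes are equally correlated. The correlations are assumptions. The concern about choosing the rule after seeing the data does not depend on them.

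**What to change.** In sections 1.5 and 3.8.3, before recruitment (planned for July 2026 in Table 22):

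- Name one already collected measure per hypothesis, with a single method of computation. Candidates are the star-test composite, countermovement jump height, and centre-of-gravity deviation in the single-leg turn. The composite in Table 18 needs a definition. Jump height needs one method, since section 3.2.2.2 uses impulse-momentum and section 3.8.2.1 uses flight time.
- Decide each hypothesis on that measure's time-by-group interaction, with Holm across the three.
- State that the Bonferroni column covers the post hoc group comparisons within an outcome.
- Report the other 16 outcomes with confidence intervals as supportive.
- Restate the power in section 3.6 for the named measures, the interaction and the adjusted level, giving the assumed correlation between time points.

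**Cost.** No new data are needed, but fewer measures can carry a confirmatory claim. At Holm's strictest step, power with 52 participants is 0.69 instead of 0.83 under ρ = 0. Restoring 80% would then take 64 completers, more than the 60 to be recruited. At an assumed ρ of 0.5, power is 0.97 and the size is adequate. Other ways of fixing the rule would also serve, provided that one is written down in advance.

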## 4.2 Jumping ability test results

Table 17 Countermovement jump (CMJ) and single-leg countermovement jump tests at baseline and after 8 weeks in the static intervention, dynamic intervention, static-dynamic intervention, and control groups. Data presented as mean  $\pm$  SD.

Group	Test Type	Time Point	Jump Height (Mean $\pm$ SD)	Peak Force (N) (Mean $\pm$ SD)	Rate of Force Development (N·s) (Mean $\pm$ SD)	Impulse (N·s) (Mean $\pm$ SD)	Two-Way Repeated Measures ANOVA	Bonferroni (p)
Static balance group	Countermovement jump	B						
		W8						
	Single-leg countermovement jump	B						
		W8						
Dynamic balance group	Countermovement jump	B						
		W8						
	Single-leg countermovement jump	B						
		W8						
Static and Dynamic balance group	Countermovement jump	B						
		W8						
	Single-leg countermovement jump	B						
		W8						
Control group	Countermovement jump	B						
		W8						
	Single-leg countermovement jump	B						
		W8						

### 4.3 Stability test results

Table 18 Eight-point Star Offset stability test results at baseline and 8 weeks postintervention in the static intervention, dynamic intervention, static-dynamic intervention, and control groups. Data presented as mean  $\pm$  SD.

Group	Test Type	Time Point	Anterior reach	posteromedial reach	composite score	Two-Way Repeated Measures ANOVA	Bonferroni (p)
Static balance group	SEBT(Pre-Test)	B					
		W8					
	SEBT(Post-Test)	B					
		W8					
Dynamic balance group	SEBT(Pre-Test)	B					
		W8					
	SEBT(Post-Test)	B					
		W8					
Static and Dynamic balance group	SEBT(Pre-Test)	B					
		W8					
	SEBT(Post-Test)	B					
		W8					
Control group	SEBT(Pre-Test)	B					
		W8					
	SEBT(Post-Test)	B					
		W8					

## 4.4 Gymnastics skills test results

### 4.4.1 Straight jump 360 ° turn test results

Table 19 Straight jump 360 ° turn test results at baseline and 8 weeks postintervention in the static intervention, dynamic intervention, static-dynamic intervention, and control groups. Data presented as mean  $\pm$  SD.

Group	Test Type	Time Point	Center of gravity deviation distance	Joint Angle variation (°)	Vertical Jump Efficiency (%)	Landing Impact Force (N)	Two-Way Repeated Measures ANOVA	Bonferroni (p)
Static balance group	Straight jump 360 ° turn (Pre-Test)	B						
		W8						
	Straight jump 360 ° turn (Post-Test)	B						
		W8						
Dynamic balance group	Straight jump 360 ° turn (Pre-Test)	B						
		W8						
	Straight jump 360 ° turn (Post-Test)	B						
		W8						
Static and Dynamic balance group	Straight jump 360 ° turn (Pre-Test)	B						
		W8						
	Straight jump 360 ° turn (Post-Test)	B						
		W8						
Control group	Straight jump 360 ° turn (Pre-Test)	B						
		W8						
	Straight jump 360 ° turn (Post-Test)	B						
		W8						

#### 4.4.2 Standing Single-leg 360 ° turn test results

Table 20 Standing Single-leg 360 ° turn test results at baseline and 8 weeks postintervention in the static intervention, dynamic intervention, static-dynamic intervention, and control groups. Data presented as mean  $\pm$  SD.

Group	Test Type	Time Point	Center of Gravity Deviation	Body Oscillation Amplitude (mm)	Rotation Smoothness Index (°)	Landing Impact Force (N)	Two-Way Repeated Measures ANOVA	Bonferroni (p)
Static balance group	Standing Single-leg 360 ° turn (Pre-Test)	B						
		W8						
	Standing Single-leg 360 ° turn (Post-Test)	B						
		W8						
Dynamic balance group	Standing Single-leg 360 ° turn (Pre-Test)	B						
		W8						
	Standing Single-leg 360 ° turn (Post-Test)	B						
		W8						
Static and Dynamic balance group	Standing Single-leg 360 ° turn (Pre-Test)	B						
		W8						
	Standing Single-leg 360 ° turn (Post-Test)	B						
		W8						
Control group	Standing Single-leg 360 ° turn (Pre-Test)	B						
		W8						
	Standing Single-leg 360 ° turn (Post-Test)	B						
		W8						

## CHAPTER 5

### 5.0 SUMMARY OF THE RESEACH PROGRESS

#### 5.1 Gantt chart and Milestone

Table 21 presents the time - planning for the PhD research project.

Table 21 Gantt chart of the research project

ACTIVITIES / MONTH	Oct 2024	Nov 2024	Dec 2024	Jan 2025	Feb 2025	Mar 2025	Apr 2025	May 2025	June 2025	July 2025	Aug 2025	Sep 2025	Oct 2025	Nov 2025	Dec 2025	Jan 2026	Feb 2026	Mar 2026
Find research topic-Refine research title and discussion of project details																		
Preparing research proposal-Journal & article search from database - Research proposal write-up -Amend proposal follow supervisor's approval																		
Submit ethical application																		
Obtain ethical approval-Amend research proposal based on ethical																		
Manuscript Preparation - Systematic Review: " Lower Extremity Injury Prevention Through Balance and Flexibility Training in Gymnastics: Meta-Analysis"																		
Manuscript Preparation - " Mechanisms of Balance State Transition Influenced by Apparatus Contact Characteristics in Gymnastics: A Systematic Review"																		

Table 21 Gantt chart of the research project (continued)

ACTIVITIES / MONTH	Apr 2026	May 2026	June 2026	July 2026	Aug 2026	Sep 2026	Oct 2026	Nov 2026	Dec 2026	Jan 2027	Feb 2027	Mar 2027	Apr 2027	May 2027	June 2027	July 2027	Aug 2027	Sep 2027
Thesis write-up-Chapters 1-3																		
Recruitment of study participants																		
Experimentation and data collection																		
Data entry and statistical analysis																		
Thesis write-up - results																		
Discussion, conclusion and abstract write-up - Submit draft to supervisor for approval and thesis amendment																		
Thesis presentation-Prepare PowerPoint slides & presenter notes																		
Thesis submission																		

## 5.2 Milestone for Research Project

Table 22 presents the key research milestones of the Research Project, along with their corresponding cumulative project completion percentages.

Table 22 Milestone for Research Project

Research Activities	Date	Cumulative Project Completion Percentage (%)
Find research topic /Literature review	1/10/2024	5
Preparing research proposal	1/1/2025	10
Obtain ethical approval	1/6/2025	15
Balance training programme and systematic evaluation of jumping and stability	1/10/2025	20
Balance training programme and cross-sectional study of jumping and stability	1/1/2026	25
Recruitment of study participants	1/7/2026	40
Experimentation and data collection	1/9/2026	70
Data entry and statistical analysis	1/3/2027	80
Final research project, presentation of data	1/5/2027	90
Submission of research project	1/8/2027	100

## **5.3 BUDGET PROPOSAL**

There is no grant available for this project. All facilities and equipment are supplied by the Beijing Sports University at no costs to the researchers.

## **5.4 ETHICAL CONSIDERATIONS**

### **5.4.1 Subject vulnerability**

In this study, participants may experience mild symptoms such as muscle fatigue, slight dizziness, or balance instability during the intervention. However, these symptoms typically subside within 24–48 hours after completing the training or testing. If participants experience any discomfort, appropriate medical care and interventions will be provided as needed.

Throughout the training and testing period, participants' safety will be closely monitored.

Medical laboratory officers and technicians trained in cardiopulmonary resuscitation (CPR) and basic life support (BLS) will always be on standby to ensure timely responses to any emergencies. Participants are free to withdraw from the study at any time without any obligations or penalties.

If these symptoms occur, they should immediately stop training and rest as needed. In the event of acute symptoms during the intervention, medical treatment will be promptly provided. Should a participant's condition worsen to the extent that hospitalization is required, the training will be suspended and resumed only after the participant's condition stabilizes. If the condition continues to deteriorate and medical professionals deem the participant unfit to continue, they will be excluded from the study to ensure their safety. The research team is committed to providing a safe environment and a supportive framework to safeguard the health and well-being of all participants throughout the study.

The participant will not be subjected to coercion or deception. All participants in this study are voluntary.

